**5.1.5 Subject Dosing and Storage Instructions (Visits 1 & 2)**

**Baseline Visit (Visit 1) and Follow-Up Visit 2**

**Visit 1 Study Medication Dosing Instructions**

Enrolled subjects will receive 2 bottles of netarsudil 0.02% at the Baseline Visit (Visit 1) and will be instructed to refrigerate both the unopened bottles (2° to 8°C [36° to 46°F]).

[REDACTED]

Subjects will return to clinic as instructed by clinic site staff for Visit 2 (Week 6) with all used/unused study medication bottles.

**Visit 2 Study Medication Dosing Instructions**

Subjects will receive 2 bottles of netarsudil 0.02% at Visit 2 (Week 6) and will be instructed to refrigerate both the unopened bottles (2° to 8°C [36° to 46°F]).

[REDACTED]

Subjects will return to clinic as instructed by clinic site staff for Visit 3 (Week 12) with all used/unused study medication bottles.

**5.2 Additional Study Supplies**

The following supplies will be provided to the study site:

- Combined Informed Consent/ Health Insurance Portability and Accountability Act of 1996 (HIPAA) form, as applicable per Institutional Review Board (IRB)
- Screening and Enrollment logs
- Electronic case report form (eCRF) completion guidelines
- Study medication reconciliation logs

- Package insert for Rhopressa (netarsudil ophthalmic solution) 0.02%

## 6.0 PRIOR AND CONCOMITANT THERAPIES

### 6.1 Allowed Medications or Treatments

Therapy considered necessary for a subject's welfare will be given at the discretion of the investigator and documented during the course of the study. The use of any concurrent medication (prescription or over-the-counter, including herbal medications) is to be recorded in a subject's source documentation (charts), as well as in the case report forms (CRFs), noting the date, dosage, frequency, start date, and reason for taking the medication(s).

## 7.0 STUDY PROCEDURES

### 7.1 Subject Entry Procedures

#### 7.1.1 Overview of Entry Procedures

Subjects meeting inclusion and exclusion criteria ([Section 4.3.1](#) and [Section 4.3.2](#), respectively) will be considered for enrollment in this study. [REDACTED]

#### 7.1.2 Informed Consent and HIPAA Authorization

Subjects meeting enrollment criteria at the Baseline Visit (Visit 1) will be asked to participate in the study. The study design, follow-up, and participation parameters/criteria will be discussed with each subject. Subjects wishing to participate must provide written informed consent and sign an "Authorization for Use and Disclosure of Health Information for Research" release as a component of the informed consent document (HIPAA authorization) prior to any study-related procedures.

#### 7.1.3 Method for Assignment of Subject ID Number

[REDACTED]

### 7.2 Study Procedures

The Schedule of Visits/Procedures for this study is included in [Appendix 4](#).

Clinical assessments will be performed throughout the study as detailed in [Section 8.0](#). All clinical assessments will be performed by the investigator (or designee).

### 7.3 Overall Instructions

Evaluations should be performed by the same evaluator throughout the study whenever possible. If this is not possible, 2 evaluators should assess the same subject simultaneously and reach agreement on results.

### 7.4 Visit 1 (Day 0): Baseline

The investigator (or designee) will perform/administer the following assessments:

- Written informed consent and HIPAA authorization
- Demographics

CONFIDENTIAL

- Subject eligibility (inclusion/exclusion criteria)
- Urine pregnancy test (if applicable)
- Medical and IOP history
- Prior and concomitant medications and/or procedures review
- Best-corrected visual acuity (BCVA)
- Biomicroscopy
- IOP assessment (measured in each eye using Goldmann applanation tonometer)
- Blood pressure measurement (sitting position)
- Corneal pachymetry to measure central corneal thickness
- Assign subject ID number
- Dispense netarsudil 0.02% and have a staff member instruct the subject on use
- Schedule Visit 2 (Week 6)

Women of childbearing potential\* must be willing to practice medically effective contraception for the duration of the study (ie, abstinence, condoms or diaphragm with spermicide, intrauterine device (IUD), or birth control pills) and must not be lactating.

*\*A woman of childbearing potential is one who has experienced menarche and who has not undergone successful surgical sterilization (hysterectomy, bilateral tubal ligation or bilateral oophorectomy), or is not postmenopausal. Postmenopausal is defined as amenorrhea for at least 12 consecutive months or a documented plasma FSH level >35 mIU/mL in conjunction with hormone replacement therapy. Women who are using oral, implanted, skin patches, or injectable contraceptive hormones, an IUD, or barrier methods (diaphragm, condoms, spermicide) to prevent pregnancy, practicing abstinence, or where partner is sterile (eg, vasectomy), are considered to be of childbearing potential.*

#### **7.5 Visit 2 (Week 6): Follow-Up**

The investigator (or designee) will perform/administer the following assessments:

- Concomitant medications and/or procedures review
- BCVA
- Biomicroscopy
- IOP assessment (measured in each eye using Goldmann applanation tonometer)
- Blood pressure measurement (sitting position)
- Adverse event (AE) assessment
- Collect used/unused study medication containers
- Dispense netarsudil 0.02% and have a staff member instruct the subject on use
- Schedule subject's next visit (Visit 3, Week 12)

#### **7.6 Visit 3 (Week 12): Final Visit**

The investigator (or designee) will perform/administer the following assessments:

- Concomitant medications and/or procedures review

- BCVA
- Biomicroscopy
- IOP assessment (measured in each eye using Goldmann applanation tonometer)
- Blood pressure measurement (sitting position)
- [REDACTED] Questionnaire
- [REDACTED] Questionnaire
- AE assessment
- Collect used/unused study medication containers
- Complete End of Study (Exit) Form

### 7.7 **Unscheduled Visits**

In the event a subject returns for an unscheduled visit, the investigator (or designee) will perform/administer necessary assessments. Information collected from an unscheduled visit will be reported on Interim/Unscheduled Visit CRF(s).

## 8.0 **CLINICAL ASSESSMENTS**

The following clinical assessments will be performed according to the schedule as indicated in the Schedule of Visits/Procedures ([Appendix 4](#)). The same investigator (or designee) should complete the evaluations for a given subject throughout the study.

### 8.1 **Efficacy Assessment**

#### 8.1.1 **Intraocular Pressure**

IOP will be measured in both eyes using a Goldmann applanation tonometer affixed to a slit lamp at the Baseline Visit, Visit 2, and Visit 3.

### 8.2 **Safety Assessments**

#### 8.2.1 **Adverse Events**

At both Visit 2 (Week 6) and Visit 3 (Week 12) the investigator (or designee) will question each subject regarding adverse experiences that may have occurred since a previous visit. Subjects will be queried "How are you feeling?" and all AEs will be recorded in the CRFs including severity, action taken, and relationship to the study medication(s) (see [Section 10.0](#) for further details).

Please see "Rhopressa Package Insert" ([Appendix 3](#)) for further details regarding possible adverse experiences associated with the use of study medication.

#### 8.2.2 **Best Corrected Visual Acuity**

BCVA will be measured for both eyes by the investigator (or designee) at the Baseline Visit (Visit 1) and at both Visit 2 (Week 6) and Visit 3 (Week 12) using a Snellen Visual Acuity Chart (see [Appendix 5](#) for detailed information on this examination).

#### 8.2.3 **Biomicroscopy**

Biomicroscopy will be performed by the investigator (or designee) for both eyes at the Baseline Visit and at each follow-up visit by slit lamp examination without pupil dilation. Eye structures/surfaces to be assessed include, but are not limited to,

lids/lashes, conjunctiva (palpebral and bulbar), cornea, anterior chamber and lens. All observations will be recorded. (see Appendix 5 for detailed information on this examination).

### **8.2.3 Pregnancy Testing**

A urine human chorionic gonadotropin (hCG) pregnancy test (only for females who are not diagnosed as postmenopausal or surgically sterile) will be used in this study and performed at the Baseline Visit to immediately confirm non-pregnancy eligibility for women of child-bearing potential.

The investigator must immediately notify the Ethics Committee/IRB and Aerie, of any pregnancy associated with the study medication exposure and keep careful source documentation of the event. In addition, the investigator must complete the pregnancy surveillance form(s) to ensure all required information is reported.

### **8.2.4 Blood Pressure Measurement**

Systemic safety assessment measured by the investigator (or designee) at the Baseline Visit (Visit 1) and at Visit 2 (Week 6) and Visit 3 (Week 12).

## **8.3 Other Assessments**

### **8.3.1 [REDACTED] Questionnaire**

An [REDACTED] Questionnaire (see [Appendix 1](#) for detailed information on this questionnaire) will be administered by the investigator (or designee) at Visit 3 (Week 12).

### **8.3.2 [REDACTED] Questionnaire**

At Visit 3 (Week 12), the investigator will complete a [REDACTED] Questionnaire (see [Appendix 2](#) for detailed information on this questionnaire).

## **9.0 END OF STUDY**

At the end of each subject's participation in the study, the investigator (or designee) will complete an End of Study Form (Completion) for all completed and discontinued subjects.

### **9.1 Completion of the Study**

Each subject who completes the entire Schedule of Visits as specified in this protocol will have completed the study.

### **9.2 Subject Discontinuation**

A subject may be withdrawn from the study prior to completion for any reason and categorized as follows:

- AEs
- Lost to follow-up
- Other (administrative reasons, etc.)

If a subject discontinues from the study for any reason at any point beyond his/her Baseline Visit (Visit 1), he/she should be requested to return for a final visit at which time all Visit 3 (Week 12) procedures should be performed according to the protocol Schedule of Visits/Procedures (see [Appendix 4](#)).

Subjects who are prematurely withdrawn or discontinued from the study will not be replaced.

### 9.3 Study Termination

The study may be terminated by the investigator or the sponsor. If, in the opinion of the investigator, clinical observations made during the study suggest that it may be unwise to continue, the investigator may stop the study. Study termination by the investigator will be reported to the sponsor.

In addition, a written statement fully documenting the reasons for this action will be submitted to the sponsor and the IRB by the investigator within 5 working days.

In the event that the sponsor chooses to discontinue or terminate the study, appropriate notification will be given to the investigator.

## 10.0 ADVERSE EVENT DEFINITIONS AND REPORTING

### 10.1 Adverse Events

An AE is defined as any untoward medical occurrence in a subject during the course of a study. An AE can, therefore, be any unfavorable and unintended sign (including a clinically significant abnormal laboratory finding), symptom, or disease temporally associated with the use of an investigational or marketed medicinal product, whether or not considered related to the investigational or marketed medicinal product. AEs include any illness, sign, symptom, or clinically significant laboratory test abnormality that has appeared or worsened during the course of the clinical trial, regardless of causal relationship to the study medication(s) under study.

Study medication is defined as a pharmaceutical form of an active ingredient or vehicle/placebo being tested or used as a reference in the study, whether masked or unmasked. AEs may be either spontaneously reported or elicited during questioning and examination of a subject.

All AEs must be completely recorded on the appropriate AE form. The severity of each AE will be graded by the investigator, using the definitions in [Section 10.1.1](#). If known, the investigator should report the diagnosis of the underlying illness or disorder, rather than its individual symptoms. Subjects experiencing AEs that cause interruption or discontinuation of study medication, or those experiencing AEs that are present at the end of their participation in the study should receive follow-up, as appropriate. If possible, report the outcome of any AE that caused permanent discontinuation or that was present at the end of the study, particularly if the AE was considered by the investigator to be related, or possibly/unlikely related to investigational product.

AEs should be followed to resolution or stabilization and reported as serious adverse events (SAEs) if they become serious ([Section 10.2](#)).

#### 10.1.1 Severity of Adverse Events

The severity of AEs will be graded by the investigator using the following definitions:

Mild: The AE is noticeable by the subject but does not interfere in a significant manner with the subject's normal functioning and is not sufficiently intense to result in medication dose reduction or discontinuation of treatment; remedial therapy may be given.

Moderate: The AE is sufficiently intense to produce some impairment of functioning and may require a reduction in medication dose or discontinuation of treatment; remedial therapy may be given.

Severe: The AE produced a significant impairment of functioning or incapacitation and may require a reduction in medication dose or discontinuation of treatment; therapy is needed.

### 10.1.2 Relationship of Adverse Events

The relationship of the AE(s) to the study medication(s) must be specified by the investigator using the following definitions:

Not Related: The event is clearly related to other factors, such as subject's clinical condition, therapeutic interventions, concomitant disease, or therapy administered to the subject and does not follow a known response pattern to the product.

Unlikely Related: The event is most probably caused by other etiologies, such as participant's underlying condition, therapeutic intervention, or concomitant therapy; or the delay between administration and the onset of the AE is incompatible with a causal relationship. Therefore, there is not a reasonable possibility that the AE was caused by the study medication.

Possibly Related: The event follows a reasonable, temporal sequence from the time of study medication administration and/or follows a known response pattern to the study medication but could have been produced by other factors, such as the subject's clinical state, therapeutic interventions, or concomitant therapy administered to the subject.

Related: The event follows a reasonable, temporal sequence from the time of study medication administration and/or follows a known response pattern to the study medication and cannot be reasonably explained by other factors, such as subject's clinical state, therapeutic interventions, or concomitant therapy administered to the subject and either occurs immediately following study medication administration, improves on stopping the study medication, reappears on repeat exposure, or there is a positive reaction at the application site.

### 10.2 Serious Adverse Events

SAEs or reactions are any untoward medical occurrence that, at any dose, meets one or more of the following criteria:

- Results in death
- Is life-threatening (defined as an event in which the subject was at risk of death at the time of the event; it does not refer to an event, which hypothetically might have caused death if it were more severe)
- Requires inpatient hospitalization or prolongation of existing hospitalization
- Results in persistent or significant disability/incapacity
- Is a congenital anomaly/birth defect
- Is an important medical event (defined as a medical event(s) that may not be immediately life-threatening or result in death or hospitalization but, based upon appropriate medical and scientific judgment, may jeopardize the subject or may require non-surgical or surgical intervention to prevent one of the other serious outcomes listed in the definition above). Examples of such events include, but are not limited to, intensive treatment in an emergency room or at home for allergic bronchospasm; blood dyscrasias or convulsions that do not result in hospitalization.

NOTE: Aerie considers all cancer AEs as SAEs.

Investigators must record all SAEs using the appropriate CRFs.

**All SAEs, whether related or unrelated to study medication, must also be immediately reported by investigators to [REDACTED] using one of the following mechanisms within 24 hours of learning of the event:**

- **Email:** [REDACTED]
- **Phone Hotline:** [REDACTED]
- **Fax:** [REDACTED]

**In addition, the governing Ethics Committee/IRB and Aerie Pharmaceuticals, Inc. (sponsor) must also be notified by telephone or confirmed facsimile transmission should an SAE occur.**

If only limited information is initially available, follow-up reports are required. Documentation of all SAEs must be maintained in the study files – eg, Serious Adverse Event Form or equivalent form (eg, MedWatch Form). Should the investigator become aware of an SAE (regardless of its relationship to investigational product) that occurs within 30 days after stopping the study medication, the SAE must be reported in accordance with procedures specified in this protocol. In the event of death, if an autopsy is performed, a copy of the report should be sent to the Ethics Committee/IRB. Aerie will report any SAEs/serious adverse device effects to other investigators, relevant competent authorities, and Ethics Committee/IRB, as required by local health care authorities.

The investigator(s) should always group signs and symptoms into a single term that constitutes a single unifying diagnosis. The investigator's opinion of the relationship of the SAE to study medication, the duration, intensity, frequency, serious criteria, countermeasures taken with study medication, and the outcome of the SAE should be documented.

### **10.3 Pregnancy**

Sexually active women of child bearing potential (See [Section 7.4](#) for definition of women of childbearing potential) must use an effective method of birth control during the course of the study, in a manner such that risk of failure is minimized. Prior to study enrollment, women of childbearing potential must be advised of the importance of avoiding pregnancy during trial participation and the potential risk factors for an unintentional pregnancy.

During the study, all women of childbearing potential should be instructed to contact the investigator immediately if they suspect they might be pregnant (eg, missed or late menstrual period). If pregnancy is suspected in any female subject while the subject is receiving study treatment, the study medication must immediately be withheld until the result of pregnancy testing is known. If pregnancy is confirmed, the study therapy will be permanently discontinued and the subject will be withdrawn from the trial. Protocol-required procedures for those subjects that are discontinued from the study must be performed on the subject unless contraindicated by pregnancy (eg, x-ray studies).

The investigator must immediately notify the Ethics Committee/IRB and Aerie, of any pregnancy associated with the study medication exposure and keep careful source documentation of the event. In addition, the investigator must complete the pregnancy surveillance form(s) to ensure all required information is reported.

## **11.0 STATISTICAL CONSIDERATIONS**

### **11.1 Sample Size**

The planned enrollment is approximately 250 subjects.

### **11.2 Analysis Populations**

An intent-to-treat (ITT) population will include all subjects who were enrolled into the study.

A modified intent-to-treat (mITT) population will include all subjects who were treated and had at least 1 follow-up visit with a completed IOP measurement.

A per-protocol (PP) population will include all subjects who completed 3 months of treatment without significant protocol violations. Subjects to be excluded from the PP analysis are subjects who have: 1) no efficacy evaluation at baseline, and/or have no follow-up visit; 2) used any prohibited medications during the study period that would interfere with the study objectives; 3) had any prohibited procedures during the study period that would interfere with the study objectives.

A safety population will include all subjects who have received at least 1 dose of study medication. This population will be used to summarize safety variables and will summarize subjects as treated.

### **11.3 Statistical Methods**

Summary tables (descriptive statistics and/or frequency distributions) will be provided for all baseline variables, efficacy variables, and safety variables. Continuous variables will be described by descriptive statistics (n, mean, standard deviation, range, and median). Frequency distributions (counts and percentage) of subjects within each category will be provided for categorical data. Additional analyses may be conducted as described in the Statistical Analysis Plan (SAP). The SAP will be finalized and approved prior to database lock.

#### **11.3.1 Baseline Analyses**

Demographic variables (age, sex, race, etc.) will be summarized by treatment group for analysis population.

Baseline characteristics (as recorded on the eCRF) will be summarized by treatment group for analysis population.

#### **11.3.2 Efficacy Analysis**

Efficacy data will be analyzed using ITT (with and without imputation of missing Week 12 assessments), mITT (without imputation of missing values), and PP populations (without imputation of missing values). No imputation will be performed for missing Week 6 values. Imputation for missing Week 12 values will be performed using the method of last observation carried forward from Week 6.

Efficacy data will be evaluated for overall, monotherapy, and concomitant participant groups.

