### 1.1 Changes from Protocol

Not applicable.

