### 3.3 Sample Size Considerations

Approximately 250 subjects will be enrolled at about 32 sites. No sample size calculation was performed.

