### 4.3 Primary Efficacy Endpoints

The primary efficacy measure is the intraocular pressure (IOP, mmHg). The primary efficacy endpoint is the percent (%) IOP reduction from baseline.

The primary efficacy analysis will be performed for mITT and PP populations. There will be no imputation for missing Week 12 assessment.

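### Enrolled subjects with no IOP after baseline enter no efficacy analysis, and the ITT rows, with or without LOCF, give little protection against attrition.

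*Protocol*

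**What the plan says.** Protocol 11.2 defines ITT as everyone enrolled and mITT as "all subjects who were treated and had at least 1 follow-up visit with a completed IOP measurement". Protocol 11.3.2 assigns imputation by population: "ITT (with and without imputation of missing Week 12 assessments), mITT (without imputation of missing values"), with PP also unimputed. It adds "No imputation will be performed for missing Week 6 values" and "Imputation for missing Week 12 values will be performed using the method of last observation carried forward from Week 6". The primary variable is percent reduction from baseline IOP.

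SAP 4.3 bases the primary analysis on mITT and PP, then says "There will be no imputation for missing Week 12 assessment". SAP 6 leaves missing data untouched by default. SAP 6 and 6.5 keep ITT efficacy summaries but give no ITT imputation rule. SAP 1.1, on changes from the protocol, reads "Not applicable". The only sensitivity analysis named (SAP 5.3 and 6.5.3) uses PP, which requires 12 weeks of completed treatment.

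Two further provisions bear on dropouts. Protocol 9.2 asks anyone who discontinues after Visit 1 to return for a final visit with all Visit 3 procedures, which include IOP. SAP 6.2.3 assigns that efficacy reading to the next scheduled visit, treats it as observed, and does so before any imputation. It also has subjects leave the study once they stop study drug.

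**The concern.** An ITT row is normally read as the result for everyone enrolled. Here it cannot be that, because the one imputation rule needs a Week 6 value that the earliest dropouts may not have. Where a dropout does have a value, it comes from Week 6 or from the exit visit, on or soon after drug. It therefore says nothing about IOP at Week 12 after stopping.

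This is a single-arm descriptive study, so the mean percent reduction is the headline result. If attrition is related to outcome, that mean is optimistic, and no planned row would show by how much. Completing 12 weeks is a condition for PP, so PP removes dropouts and does not test the result against their loss.

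**Working it through.** **No plan figure to reproduce.** Protocol 11.1: "The planned enrollment is approximately 250 subjects". SAP 3.3: "No sample size calculation was performed". Neither document gives a dropout rate, an expected percent reduction or an SD, so every size below is an illustration.

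**Step 1: who has a Week 12 value.**

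- *Stops before Week 6, no exit IOP:* no value under either rule, so in no efficacy row.
- *Stops before Week 6, attends exit:* the exit IOP becomes Week 6. Protocol LOCF carries it to Week 12; without imputation Week 12 stays missing.
- *Stops after Week 6, no exit IOP:* LOCF uses Week 6; without imputation Week 12 is missing.
- *Stops after Week 6, attends exit:* the exit IOP counts as observed Week 12 under both rules.

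A subject in ITT but not mITT has no follow-up IOP, apart from the unlikely case of a never-dosed subject with one. The two unimputed rows therefore hold the same values. A simulated set of 250 with 22 early and 20 late dropouts and no exit visits confirms it: both unimputed rows have n = 250 - 22 - 20 = 208 and a mean of 21.01%. ITT-LOCF has n = 250 - 22 = 228 and a mean of 21.14%.

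**Step 2: number with no value.** Formula: 250 x dropout x share leaving before Week 6 x (1 - exit attendance).

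| Dropout (assumed) | Share before Week 6 (assumed) | No attendance | 50% | Full |
|---|---|---|---|---|
| 10% | 40% | 250 x 0.10 x 0.40 = 10 | 5 | 0 |
| 20% | 70% | 250 x 0.20 x 0.70 = 35 | 17.5 | 0 |

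**Step 3: effect on the mean.** Assume a 20% reduction in those observed (for scale, 5 mmHg from 25 mmHg). Counting all dropouts at 0% gives 20% x 0.90 = 18% at 10% dropout and 20% x 0.80 = 16% at 20% dropout.

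Now take 20% dropout, half before Week 6: 200 completers, 25 early and 25 late dropouts. Let the dropouts' last on-drug reduction be 20% or 10%.

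| Last on-drug reduction | Exit attendance | No imputation (ITT = mITT) | ITT-LOCF | All 250, dropouts at 0% |
|---|---|---|---|---|
| 20% | none or full | 20.0% | 20.0% | 16.0% |
| 10% | none | 20.0% (n = 200) | (200x20 + 25x10)/225 = 18.9% | 16.0% |
| 10% | full | (200x20 + 25x10)/225 = 18.9% | (200x20 + 50x10)/250 = 18.0% | 16.0% |

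LOCF and exit mapping move the estimate when dropouts responded poorly before stopping. They do nothing about effect lost after stopping.

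**Step 4: scale.** With an assumed SD of 10 to 20 percentage points, the 95% half-width at n = 250 is 1.96 x SD / sqrt(250) = 1.2 to 2.5 points. A gap of 2 to 4 points is of that order or larger.

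**Step 5: a conflict in the exit rule.** An exit after Visit 2 but by Day 63 goes to Week 12 under SAP 6.2.3. Under the SAP 6 window (Day 2 to Day 63) it belongs to Visit 2, where the record nearest the target date is used. Whether such a dropout has a Week 12 value depends on which rule is applied.

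**The case against.** The strongest answer is that dropouts are provided for. Exit visits are requested from everyone who stops after baseline, their IOP counts as observed data, and LOCF covers late dropouts who do not return. This stands against the stronger inference that ITT gives no protection at all, or that no analysis reflects subjects who stopped. But attendance is only requested, loss to follow-up is one of the three listed discontinuation categories, and the readings kept are from on or soon after drug.

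Other inferences a reader might draw also go too far:

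- *That agreement between ITT and mITT is always built in.* It is for the unimputed rows. The protocol plans mITT without imputation only, so ITT-LOCF against mITT is a real comparison (228 against 208 in the simulated set).
- *That the SAP has expressly dropped LOCF.* Its no-imputation sentence follows directly on mITT and PP, for which the protocol also has none. For ITT, the omission is inferred from the default on missing data and from the absence of a rule. SAP Module II was not available, and parts of the public SAP are blank.
- *That most dropouts leave because of side effects or poor response.* The documents give no reasons by frequency, and their categories include none for lack of efficacy.

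It is also fair that the study is descriptive, with no hypothesis test in the visible text, and that ITT is not part of the SAP's primary analysis. No type I error is at stake; the risk is an optimistic mean.

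**Conclusion.** The point holds in limited form. Protection against attrition is little: none for subjects with no post-baseline IOP, and none against loss of effect after stopping. The visible SAP does not carry over the protocol's ITT-LOCF analysis, and SAP 1.1 does not list this as a change.

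The true size cannot be fixed from the documents. A gap of 2 to 4 points rests on a 20% reduction in those observed, 10-20% dropout and full return to baseline. It is the gap from a planned row still at 20%, and it shrinks where poor responders' last values are retained. The count of 10 to 35 subjects with no value is the no-attendance end of a range that starts at zero, so it should not be read as a forecast.

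**What to change.** 1. In SAP 6.5.3, add one ITT Week 12 sensitivity analysis in which every enrolled subject who stopped treatment or has no Week 12 IOP is counted at baseline (0% reduction). Label it a conservative bound. No washout is required when prior therapy is replaced (protocol 5.1.4), so baseline may be on earlier treatment, and some missed visits are not failures.
2. Report the number of subjects contributing to every efficacy row.
3. State the ITT imputation rule in the SAP, or list its removal in SAP 1.1.
4. Reconcile the exit mapping in SAP 6.2.3 with the Day 2 to Day 63 window in SAP 6.

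The cost is one extra table, a few sentences and a less favourable ITT figure. A repeated-measures model on Weeks 6 and 12 is optional. In its usual form it still omits subjects with no post-baseline IOP and estimates the effect as if dropouts had stayed on treatment, so it does not replace item 1.
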